- For comparison of independent samples, the Pearson's Chi-squared test or the Fisher's exact test for 2x2 tables or likelihood ratio for mXn tables will be used for qualitative variables. The Student's t-test, one-way ANOVA or its non-parametric equivalents, the Mann-Mann U test or Kruskal-Wallis H test, will be used for quantitative variables.
- For comparison of paired samples, the McNemar's test will be used for qualitative variables and the Student's t-test or Wilcoxon's test for quantitative variables.
- The study will seek to identify factors associated with the occurrence of exacerbations throughout the follow-up period; to that end, a multivariate logistic regression analysis will be performed, where the dependent variable will be the occurrence of exacerbations (Yes/No) during the study. Vaccination with PCV13 and significant variables in the univariate model will be used as possible risk factors: demographic characteristics, influenza vaccination, smoking habit, etc. In addition, potential confounding variables will be considered: exacerbator phenotype, comorbidities, COPD severity, FEV1 (no control possible based on the study design).
- Appropriate tests will be performed accordingly to determine if the necessary requirements are fulfilled for the use of parametric tests.
- Estimates will be performed with a 95% confidence interval. The SPSS statistical package, version 19.0 or later, will be used.

8.2 **STATISTICAL ANALYSIS**

8.2.1 **Patient disposition**

The absolute and relative frequency of evaluable patients will be determined. In the subpopulation of non-evaluable patients, the frequency distribution will be presented based on the reasons for non-evaluation:

- Patient under 18 years of age at the time of obtaining informed consent
- Not diagnosed with COPD of any grade (patients diagnosed with COPD less than 2 years after inclusion in the study should not be included)
- At least two years of prior medical records are not available relating to (if applicable):
 - History of moderate/severe exacerbations
 - History of influenza vaccination (date)
 - History of pneumococcal vaccination (date)
 - Comorbidities
 - Previous treatments
- No spirometry data available
- Inability to understand and complete the required quality of life questionnaires
- No evidence of a personally signed and dated informed consent document indicating that the subject has been informed of all pertinent aspects of the study

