The Student's t test, one-way ANOVA or its non-parametric equivalents, the Mann-Mann U test or Kruskal-Wallis H test will be used to determine if statistically significant differences are observed in NEPA, NEPA Mild, NEPA Moderate, NEPA Severe and NEPA Moderate/Severe according to the severity of COPD and type of patient (exposed/unexposed). In order to determine the impact of PCV13 vaccination on exacerbations, paired data comparisons will be made between (NEPA_pre_PCV13 vs. NEPA_post_PCV13) and (NEPA_pre_PCV13 (moderate/severe) vs. NEPA_post_PCV13 (moderate/severe)), using the Student's t-test for paired data or its non-parametric equivalent, the Wilcoxon test.

In order to study which subgroups of patients obtain a greater benefit from vaccination

with PCV13 according to COPD severity, paired data comparisons will be made between (NEPA_pre_PCV13 vs. NEPA_post_PCV13) and (NEPA_pre_PCV13 (moderate/severe) vs. NEPA_post_PCV13 (moderate/severe)), in each of the four patient subpopulations established based on disease severity.

In order to determine the factors associated with the presence of an exacerbator patient, a logistic regression model will be constructed, whose dependent variable is (exacerbator/non-exacerbator patient) and, as independent variables, all those possible factors that have been significant in the univariate models ($p_{value} < 0.25$), following the methodology of Hosmer-Lemeshow.

- ❖ Vaccine exposure (PCV13 yes/no)
- ❖ COPD severity (Grade I, Grade II, Grade III, Grade IV)
- ❖ Age
- ❖ Sex
- ❖ Time since diagnosis of the disease
- ❖ Patient with stable treatment for at least three months
- ❖

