8.2.3.2 Change in post-bronchodilator spirometry test

Changes in the spirometry data at the different follow-up visits will be given and analyzed using the main measures of central tendency and dispersion (mean, median, standard deviation, confidence intervals, minimum, maximum and interquartile range).

- FEV1
- FVC
- FEV1/FVC

The study will examine whether there has been a significant change in the spirometry data over time, both in the total sample of evaluable patients and in each of the subpopulations established based on the severity of the COPD and type of patient, using the Student's t-test for paired data or its non-parametric equivalent, the Wilcoxon test. The % reduction in the parameters FEV1, FVC and FEV1/FVC will be calculated at the 24-month visit relative to baseline ((final value-baseline value)*100/baseline value).

The Student's t-test, one-way ANOVA or its non-parametric equivalents, the Mann-Mann U test or Kruskal-Wallis H test will be used in order to determine if statistically

significant differences in FEV1, FVC, FEV1/FVC (% reduction compared to the FEV1, FVC and FEV1/FVC baseline values) are observed, depending on the severity of the COPD and type of patient (exposed/unexposed).

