The change in the quality of life of the patients according to the Saint George's questionnaire will be studied, presenting the main measures of central tendency and dispersion (mean, standard deviation, median, minimum, maximum, IR and 95%CI), both for the total score obtained and for the three domains of Symptoms, Activity and Impacts. We will explore whether there are statistically significant differences in the quality of life of patients depending on the severity of COPD and the type of patient using the Student's t-test or its non-parametric equivalent Mann-Whitney U test, depending on the distribution of the variables.

We will examine whether there has been a significant change over time in quality of life, both for the total sample of evaluable patients and in each of the subpopulations established based on the severity of COPD and the type of patient, using the paired Student's t-test or its non-parametric equivalent, the Wilcoxon test.

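### FEV1 and quality of life are compared between non-randomised vaccinated and unvaccinated patients with no covariate adjustment, so an apparent vaccine effect on two secondary objectives could be created or masked

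*SAP*

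**What the plan says.** **FEV1.** SAP 8.2.3.2 states: "The % reduction in the parameters FEV1, FVC and FEV1/FVC will be calculated at the 24-month visit relative to baseline", with the formula "final value-baseline value)*100/baseline value". The percent "reduction compared to the FEV1, FVC and FEV1/FVC baseline values" is compared by exposure and by severity with t-test or ANOVA, or their rank equivalents. No covariate is named.

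**SGRQ and CAT.** SAP 8.2.3.7.1 looks for "differences in the quality of life of patients depending on the severity of COPD and the type of patient using the Student's t-test" or the Mann-Whitney test, and 8.2.3.7.2 does the same for CAT. Neither section says whether the tested variable is a change or a raw score, or at which visit. Both name only two-sample tests, although severity has four grades. SAP 8.1 lists ANOVA and Kruskal-Wallis.

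**Multivariable models.** There are two, both logistic and both for exacerbations. SAP 8.1 has one "where the dependent variable will be the occurrence of exacerbations (Yes/No) during the study". SAP 8.2.3.1 has one "whose dependent variable is (exacerbator/non-exacerbator patient"). The potential confounders in 8.1 include "COPD severity, FEV1 (no control possible based on the study design"). No regression, matching or weighting is planned for FEV1 or quality of life.

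**Design.** Under Protocol 8.2 (Study procedures), vaccination follows clinical practice and may precede or follow inclusion. Protocol 8.1 lists among the controls patients who received no recommendation, patients who did not take it up, and patients with contraindications. Protocol Table 1 schedules spirometry and quality of life at months 0, 12 and 24.

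**The concern.** The exposure groups were not formed by chance. They may differ in severity, age, smoking or site, and each of these can affect lung function and quality of life. An unadjusted two-sample test attributes the whole difference to exposure. The SAP recognises this risk for exacerbations but provides nothing for these outcomes. SAP 8.2.2 does not compare baseline FEV1 or quality-of-life scores between exposure groups, so those tables would not show an imbalance in them.

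Percent change uses each patient's own baseline, but baseline sits in both numerator and denominator. A group whose baseline was low partly through measurement error will appear to do better later. For SGRQ and CAT the problem depends on what is tested: a raw score carries the imbalance straight through, and a change score is open to regression to the mean.

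Secondary objectives 2 (quality of life) and 3 (FEV1) are at stake. The primary exacerbation analysis is not touched by this point.

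**Working it through.** **No planned figure to reproduce.** The sample-size text (Protocol 8.5, SAP 5) covers exacerbations only. It supplies the group sizes: 540 × 0.7 = 378 and 378 × 0.7 = 264.6 (stated as 264) exposed; 1000 × 0.7 = 700 and 700 × 0.7 = 490 unexposed. Month 24 therefore has 264 + 490 = 754 patients. Everything else below is an assumption.

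**Step 1. Normal approximation, no vaccine effect, two-sided 0.05 (relevant to SGRQ and CAT).** Let d be the baseline imbalance in SDs and r the baseline to month-24 correlation.

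- k = √(1/264 + 1/490) = 0.0763.
- If the imbalance regresses: the difference in change is (1−r)d with SE k√(2(1−r)), and the difference in raw month-24 score is rd with SE k.
- If the imbalance is stable: the difference in change is 0, the difference in raw score is d, and ANCOVA is off by (1−r)d with SE k√(1−r²).

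Example for d = 0.2, r = 0.8, change score with regression: 0.2 × 0.2 = 0.04; SE = 0.0763 × √0.4 = 0.0483; z = 0.83; rejection 13%.

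| d = 0.2 | r = 0.5 | r = 0.7 | r = 0.9 |
|---|---|---|---|
| Imbalance regresses: change score | 26% | 17% | 9% |
| Imbalance regresses: raw score | 26% | 45% | 66% |
| Imbalance stable: change score | 5% | 5% | 5% |
| Imbalance stable: raw score | 75% | 75% | 75% |
| Imbalance stable: ANCOVA | 33% | 20% | 9% |

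With d = 0 every entry is 5%.

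**Step 2. FEV1 percent change, simulated with the imbalance regressing** (assumed mean 60, SD 18; 264 v 490; 2000 runs per setting).

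| d | r | Apparent benefit, percentage points | t-test | Mann-Whitney | ANCOVA |
|---|---|---|---|---|---|
| 0.2 | 0.9 | 0.6 | 8% | 7% | 5% |
| 0.2 | 0.7 | 2.3 | 19% | 15% | 5% |
| 0.3 | 0.9 | 0.9 | 13% | 10% | 5% |
| 0.3 | 0.7 | 3.6 | 37% | 28% | 5% |

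**Step 3. Let vaccination depend on FEV1 in two ways** (754 patients, no vaccine effect; assumed mean 58, SD 18, reliability 0.85; log-odds of vaccination 0.2 or 0.4 higher per SD lower FEV1).

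| Vaccination follows | Percent-change t-test, 0.2 / 0.4 | ANCOVA, 0.2 / 0.4 |
|---|---|---|
| Measured visit 0 value, error included | 8% / 24% | 4-5% |
| True, stable severity | 5% / 6% | 9% / 27% |

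Other runs of this design, with different choices for details such as assumed decline or a floor on FEV1, gave 8-11% and 19-28% for the t-test in the first row. In the second row they gave about 6% at both slopes for the t-test and 10% / 24% for ANCOVA. The ordering of the two methods reverses between the rows each time.

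**Step 4. Unused data.** Planned numbers fall from 378 + 700 = 1078 at year 1 to 754 at year 2. About 1078 − 754 = 324 patients with a scheduled month-12 value would contribute nothing to the month-24 FEV1 comparison.

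**The case against.** The strongest reply is that FEV1 is already expressed relative to each patient's own baseline and that nothing in the documents shows vaccination tracking severity. The guideline cited in the protocol recommends PCV13 across mild, moderate and severe COPD. With no imbalance, the tests hold their 5% level. If vaccination follows stable severity, percent change is close to nominal and ANCOVA is the worse method. Where vaccination preceded inclusion, measurement error at visit 0 cannot have driven it. That baseline is also post-exposure, so adjusting for it could remove part of a real effect.

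Most of this stands, and it limits the point. It does not supply the missing adjustment for severity, age, smoking or site. SAP 8.2.1 splits the analyses by exposure and by severity, but no exposed-unexposed comparison within grade is stated.

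Four stronger readings are tempting and are not supported:

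- **That the bias favours the vaccine.** Vaccinated patients who start better would show a spurious harm, or a real benefit would be hidden.
- **That ANCOVA is the cure.** Step 3 shows that it can be the more biased method.
- **That baseline is ignored for FEV1.** It is used, but imperfectly.
- **That naming two-sample tests for four grades inflates the family-wise error by a known amount.** The SAP specifies no set of pairwise tests, and 8.1 already lists the multi-group tests. This is a wording conflict, and grade comparisons say nothing about a vaccine effect.

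**Conclusion.** The point holds in this form: no covariate-adjusted comparison of FEV1, SGRQ or CAT between exposure groups is planned in a non-randomised cohort, and the quality-of-life variable and visit are unspecified. This follows from the text and needs no assumption.

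The size cannot be fixed from the documents. Under the Step 3 assumptions, the false-positive rate of the FEV1 test runs from about nominal (5-6%) to 24%, depending on what drives vaccination. For quality of life at an assumed imbalance of 0.2 SD, it runs from 5% for a change score under stable imbalance to 75% for a raw score under persisting imbalance. The direction may be either way. Only secondary objectives are affected, so the change should be made but does not threaten the primary analysis.

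**What to change.** 1. For FEV1, SGRQ and CAT, fit a linear mixed model to months 12 and 24 with exposure, visit, baseline value, GOLD grade, age, sex, smoking, influenza vaccination and site. Month-12 values of patients lost in year 2 then contribute. State how exposure is coded for patients vaccinated between visits.
2. Report a covariate-adjusted change-score model beside it as a sensitivity analysis, because the two rest on different assumptions about the imbalance.
3. Analyse patients vaccinated before visit 0 separately, since their baseline is post-exposure.
4. State that the quality-of-life outcome is the month-12 and month-24 score adjusted for baseline.
5. In SAP 8.2.3.7.1 and 8.2.3.7.2, replace the two-sample tests for the four-grade comparison with the ANOVA or Kruskal-Wallis test of SAP 8.1.

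The required variables are already scheduled for collection, so the cost is SAP wording and modest extra analysis. The downside is that the two models may disagree. If so, both must be reported and the disagreement discussed.

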8.2.3.3 Smoking habit

The study will explore if there have been changes in the patients' smoking habit during the follow-up, presenting the frequency distribution of the patients for each of the study visits according to the smoking habit described in said visit.

- Regular smoker (currently smokes tobacco daily)
 - How many cigarettes per day? Mean (SD)
- Occasional smoker (does not smoke daily)
- Never-smoker: Has not been exposed to smoking.
- Former smoker: Has quit smoking more than 6 months ago.
 - Pack-years: Mean (SD)

Both for the total sample of evaluable patients and for each of the analysis subpopulations, the study will determine whether there has been significant change during the study in terms of the patient's smoking habit, using the sign test.

In order to determine whether there are statistically significant differences in smoking habits in patients, depending on the severity of COPD as well as on the type of patient (exposed/unexposed), the Pearson's Chi-squared test or the Fisher's exact test for 2x2 tables or likelihood ratio for mXn tables will be used.

8.2.3.4 COPD treatment

A detailed descriptive analysis of the treatments used by COPD patients will be performed. The absolute and relative frequency of patients who have received any of the following at some point during the disease will be given:

- Short-acting bronchodilators
 - Anticholinergics (SAMA) (ipratropium bromide, umeclidinium)
 - Short-acting β -2 agonists (SABA) (salbutamol, terbutaline)
- Long-acting bronchodilators
 - β -2 adrenergics (LABA) (salmeterol, formoterol indacaterol, vilanterol, olodaterol)
 - Anticholinergics (LAMA) (tiotropium bromide, aclidinium, glycopyrronium, umeclidinium)

- LABA+ LAMA
- Theophyllines
 - Theophylline +LABA+LAMA
 - Purified α -1-antitrypsin (AAT) replacement therapy
- Inhaled corticosteroids (IC): budesonide, fluticasone propionate, fluticasone furoate, beclomethasone, ciclesonide
 - IC+LABA
 - IC+LAMA
 - IC+LABA+LAMA
 - IC+ Theophylline
- Phosphodiesterase 4 (PDE4) inhibitors (Roflumilast)
 - PDE4 inhibitor+LABA
 - PDE4 inhibitor+LAMA
 - PDE4 inhibitor+LABA+LAMA
 - N-acetylcysteine (NAC)
- Antibiotics
 - Macrolides
 - Quinolones
- Other _____ specify

Additionally, the compliance of the patient will be described for each of the study progress visits through frequency distribution:

- ▣ Complies with treatment
- ▣ Does not comply with treatment
- ▣ Probably complies with treatment.

Using the Pearson's Chi-squared test or the Fisher's exact test for 2x2 tables or likelihood ratio for mXn tables, the study will examine whether there are statistically significant differences in the use of each of the treatments and the compliance of the patient according to the different analysis groups.

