**TABLE 1. FOLLOW UP VISITS**

	Visit	0	1	2	3	4	5
	Month	0	1	6	12	18	24
Verification of inclusion/exclusion criteria		X	X	X	X	X	X
Informed consent signature		X					
Demographic variables		X					
Exacerbations and smoking history		X	X	X	X	X	X
Clinical history (hospital and/or primary care)		X					
Performance or verification of recent spirometry		X			X		X
Completion of QOL test		X			X		X
Treatment and vaccination recommendations adjustment (as per normal clinical practice)		X			X		X
Telephone Follow up (if applicable)				X		X	
PCV13 vaccination record			X		X		X
Influenza vaccination record			X		X		X
Updated treatment record			X		X		X

**Definitions:**

- COPD exacerbations are defined as a complex of two or more respiratory symptoms (worsening dyspnea, cough, sputum production, chest tightness, or wheezing) related to the underlying COPD, with duration of 3 days or more, that require a change in treatment.
  - *Treatment changes* include acute treatment with antibiotics and/or steroids, or an addition of new maintenance bronchodilator.
  - *Mild exacerbations* are those that require new prescription of bronchodilator only
  - *Moderate exacerbations* are those that require antibiotics and/or systemic corticosteroids without hospitalization,
  - *Severe exacerbations* are those that lead to hospitalization.
- The onset date of exacerbations is defined by the onset of the first recorded symptom.
- Exacerbations that occur within 7 days of onset of a prior exacerbation are counted as a single exacerbation

A subject presenting with exacerbation, will be considered as vaccinated at least 15 days after receiving immunization

Redacted

- Immunosuppression:
  - Lymphoma/Leukemia
  - Another neoplasm subjected to immunosuppressing treatments
  - Organ transplant with its corresponding immunosuppressing treatment
  - Leukopenia<1.000/mm; neutropenia<500/mm
  - Patients infected by Human Immunodeficiency Virus (HIV)
  - Congenital immunodeficiency
  - Diseases that requires continuous treatment with systemic corticosteroids administration for more than 14 days (prednisone at doses> 15 mg/day or other equivalent preparations), or cytotoxic agents during the previous six months.

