- Impossibility to perform prospective follow-up
- Present any immunocompromising condition

- Present any other respiratory disease as comorbidity

In the subpopulation of evaluable patients, the frequency distribution will be given according to the analysis groups:

Exposed/unexposed patient:

- Patient with COPD of any grade vaccinated with PCV13
- Patient with COPD of any grade not vaccinated with PCV13

In the subpopulation of exposed patients and provided that we have a sufficient frequency, a new analysis group will be established based on:

- **PCV13 only**
- **PCV13+ PPV23**
- **PCV13+ Influenza (same summer period)**
- **PCV13+ PPV23+influenza (same summer period)**

COPD severity:

- GRADE 1: Mild/unknown [$FEV1 \geq 80\%$, $FEV1/FVC < 0.7$ or no spirometry record]
- GRADE 2: Moderate [$50\% \leq FEV1 < 80\%$, $FEV1/FVC < 0.7$]
- GRADE 3: Severe [$30\% \leq FEV1 < 50\%$, $FEV1/FVC < 0.7$]
- GRADE 4: Very severe [$FEV1 < 30\%$ or $FEV1 < 50\%$ plus respiratory failure, $FEV1/FVC < 0.7$])

The statistical analysis detailed below will be performed both with the total sample of evaluable patients and divided based on the two analysis groups established: exposed/unexposed and severity of COPD.

Additionally, a flow chart will be presented on the total number of patients analyzed at each of the study follow-up visits:

- Month 1
- Month 6
- Month 12
- Month 18
- Month 24

In the subpopulation of ineligible patients at each of the scheduled visits, the frequency distribution will be given based on the reason for ineligibility:

- Does not meet one or more of the inclusion criteria:
 - a) Aged ≥ 18 years at the time of obtaining informed consent
 - b) Diagnosed with COPD of any grade
 - c) With at least 2 years of previous clinical history available relating to (if applicable): history of moderate/severe exacerbations, history of influenza vaccination (date), history of pneumococcal vaccination (date), comorbidities and previous treatment
 - d) Spirometry data (if available at enrollment, should be a maximum of 6 months old. If not available at enrollment, perform as per routine clinical practice at visit 1 ± 1 month.
 - e) Ability to understand and complete the required quality of life questionnaires
 - f) Existence of a personally signed and dated informed consent document indicating that the subject has been informed of all pertinent aspects of the study
- Meets one or more of the inclusion criteria:

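### COPD treatment is compared between cohorts as any use during the disease, so the table pools earlier treatment with antibiotics given for the endpoint, and no dated treatment balance check or adjustment is pre-specified

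*SAP*

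**What the plan says.** SAP 8.2.3.4 presents the frequency of patients who "have received any of the following at some point during the disease will be given". The list holds maintenance classes (long-acting bronchodilators, inhaled corticosteroids, PDE4 inhibitors), short-acting bronchodilators, and antibiotics (macrolides, quinolones). It does not separate long-term from acute use, or use before vaccination from use after it. The section then looks for "significant differences in the use of each of the treatments and the compliance of the patient according to the different analysis groups". SAP 8.2.1 states that the analyses are run on the whole sample and "divided based on the two analysis groups established: exposed/unexposed and severity of COPD".

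The definitions under Table 1 of the protocol (8.3.1) make a treatment change part of an exacerbation. Qualifying changes "include acute treatment with antibiotics and/or steroids, or an addition of new maintenance bronchodilator". Moderate exacerbations "are those that require antibiotics and/or systemic corticosteroids without hospitalization". An event needing only a new bronchodilator is mild.

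SAP 8.2.2 describes demographics, body measurements, alcohol and medical history at baseline, but not treatment. The only treatment-related candidate for the logistic model in SAP 8.2.3.1 is "Patient with stable treatment for at least three months", with no date attached. SAP 8.1 names exacerbator phenotype, comorbidities, COPD severity and FEV1 as potential confounders, and names no drug class.

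Umeclidinium appears in two classes of the treatment list: "Anticholinergics (SAMA) (ipratropium bromide, umeclidinium" and "Anticholinergics (LAMA) (tiotropium bromide, aclidinium, glycopyrronium, umeclidinium".

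**The concern.** Vaccination follows routine practice (Protocol 8.2), and the controls include patients who were not recommended the vaccine, did not take it up or had a contraindication (Protocol 8.1). Treatment intensity may therefore differ between the cohorts, and it may go with exacerbation risk. A reader will want to know whether treatment was similar before exposure.

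The planned table cannot answer that. A patient given a quinolone for an exacerbation during follow-up counts exactly like one who took it years before vaccination. If the cohorts differ in exacerbations, through a vaccine effect, through confounding or by chance, the antibiotic rows will tend to differ too. The table can show an imbalance that was not there at the start, or hide one that was. Using these any-time variables for adjustment would mean conditioning partly on the outcome.

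Other variables in the SAP are anchored in time: smoking and compliance by visit, spirometry relative to baseline. Drug use is not.

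**Working it through.** The plan states no figure for this table, so what follows is an illustration.

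**Inputs from the documents.** Moderate/severe exacerbation by 2 years: 60% of 264 exposed and 74% of 490 unexposed patients (Protocol 8.5; SAP 5). By 1 year: 27% of 378 and 37% of 700. Significance level 0.05, taken as two-sided because the SAP does not say.

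**Assumed inputs.** *b* is the share with any listed antibiotic before follow-up, set equal in both cohorts so that there is no true imbalance. *s* is the share of patients with an event who receive a listed antibiotic for it, also equal in both. Prior use is taken as independent of later events.

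**Formula.** Any-time use = b + (1 − b) × p × s, where p is the event rate. The gap between cohorts is (1 − b) × s × (0.74 − 0.60).

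For b = 0.30 and s = 0.50:
- exposed: 0.30 + 0.70 × 0.60 × 0.50 = 51.0%
- unexposed: 0.30 + 0.70 × 0.74 × 0.50 = 55.9%
- gap: 4.9 points

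**Chance of p < 0.05.** Φ[(gap − 1.96 × SE0) / SE1], where SE0 is the pooled and SE1 the unpooled standard error of the difference. For the case above, SE0 = 0.0380 and SE1 = 0.0381, so (0.049 − 0.0746) / 0.0381 = −0.67, which gives 25%. Applied to the planning table, this method gives 91.9% at year 1 against the stated 91.43%. At year 2 it gives 97.5% against the stated 91%. That mismatch is a separate matter; only the planned rates and group sizes are used here.

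| b | s | Exposed | Unexposed | Gap (points) | Chance of p < 0.05 |
|---|---|---|---|---|---|
| 10% | 50% | 37.0% | 43.3% | 6.3 | 39% |
| 10% | 90% | 58.6% | 69.9% | 11.3 | 88% |
| 30% | 50% | 51.0% | 55.9% | 4.9 | 25% |
| 30% | 90% | 67.8% | 76.6% | 8.8 | 74% |
| 90% | 50% | 93.0% | 93.7% | 0.7 | 6% |
| 90% | 90% | 95.4% | 96.7% | 1.3 | 15% |

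Every gap comes from the endpoint alone. With the 1-year rates and b = 30%, the gap is 3.5 to 6.3 points and the chance 20% to 51%.

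**The reverse error.** Suppose prior use truly differs, 40% exposed v 30% unexposed (assumed). A table at a fixed index date would detect this with 79% power at 264 v 490. In the any-time table after 2 years:
- s = 0.5: 58.0% v 55.9%, +2.1 points, 8% chance of significance
- s = 0.7: 65.2% v 66.3%, −1.1 points, 5%
- s = 0.9: 72.4% v 76.6%, −4.2 points, 25%

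In the last two cases the difference points the wrong way.

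**The case against.** The strongest reply is that SAP 8.2.3.4 calls itself a descriptive analysis, sits among the effectiveness results and is never presented as a balance check. No exacerbation test uses it. This stands as to purpose. But the section does test each class between exposed and unexposed patients, and no other table compares treatment between them.

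The size is also open to challenge. The documents give neither b nor s. The SAP names only macrolides and quinolones, and an event can qualify on systemic corticosteroids alone, so s may be below 50%; at s = 0.30 and b = 0.30 the gap is 0.70 × 0.30 × 14 = 2.9 points. Prior use may also be high after years of disease. At 37% a year with s = 0.7, and independent years, any-time use reaches 1 − (1 − 0.259)^4 = 70% after four years and 95% after ten. A false imbalance then becomes unlikely, but the rows also saturate and say little.

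A reader might infer four stronger things that the documents do not support:
- **That the whole table re-counts the endpoint.** Direct overlap with moderate/severe events lies in the antibiotic rows. Bronchodilator-only changes define mild events, and systemic corticosteroids are not a listed class.
- **That the primary estimate is wrong because of this table.** The tests of exacerbations per patient-year in SAP 8.2.3.1 do not draw on it.
- **That the models rule out treatment adjustment.** The covariate list in SAP 8.1 ends openly, SAP 8.2.3.1 admits factors that pass a univariate screen, and severity and FEV1 would absorb part of any treatment difference. Adjustment is possible but not pre-specified.
- **That every umeclidinium user is counted twice.** The drug is listed in two classes, but the documents do not show how the CRF maps it.

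**Conclusion.** The concern holds in limited form. The any-time window makes the cohort comparison of treatments uninterpretable as a check of imbalance, most clearly in the antibiotic rows, and the plan neither provides another check nor pre-specifies adjustment for maintenance treatment. The harm is a misleading comparison and a likely source of uncontrolled confounding, not a direct error in the primary result.

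With identical prior use of 30% and s of 50-90%, the planned event rates alone create a 4.9-8.8 point gap with a 25-74% chance of significance. Over prior use of 10-90% the gap is 0.7-11.3 points and the chance 6-88%. These figures rest on assumed b and s and on the planned 14-point event difference. The documents give nothing from which to size the residual confounding in the exacerbation results, so no number is put on it. The text should be changed before analysis.

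**What to change.** In SAP 8.2.3.4, replace the any-time window with:
- the maintenance regimen at a fixed index date: enrolment for all patients and, for exposed patients, also the last regimen before vaccination where the 2-year history covers it;
- the regimen at visits 1, 3 and 5.

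Report antibiotic courses given for exacerbations separately, where the CRF records purpose or duration. Enter index-date maintenance class as a fixed covariate in the logistic models, and take the three-month stability variable at the same date. Reconcile the two class entries for umeclidinium.

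Two limits should be written into the SAP. Patients may be vaccinated before inclusion (Protocol 8.2), so for them enrolment treatment is post-exposure and cannot show balance before vaccination. Also, exacerbations per patient-year are counted from COPD diagnosis (SAP 8.2.3.1), so enrolment falls inside the counted period, and those cohort tests remain unadjusted for treatment.

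The cost is mainly SAP wording and derived variables. Previous treatments are part of the required history (Protocol 8.2.1; SAP 5.1.1), and Table 1 of the protocol records updated treatment at visits 1, 3 and 5. The models gain a few parameters. Coding antibiotic purpose takes some work and may not be possible if the CRF, which is not among the documents reviewed, does not record it.
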